Assessment schedule	
 • Subject inclusion (subject demography, surgery, hospital discharge)

	
 • 1-3 month post implant • 1 year post implant • Yearly up to 5 years

Statistical considerations
	
The study includes an adaptive approach for the determination of the study sample size.
 
Primary analysis
 
The primary study objective will be investigated by the primary analysis comparing the primary endpoint between the two randomized groups on PP population defined as all subjects without major protocol deviations and attending the scheduled follow-up visits up to 1 year at minimum.
 
A one-sided non-inferiority test will compare the two arms on the proportion of subjects that are event-free at one year.
 
The null hypothesis is that the 1-year freedom from MACCE in the Perceval arm is inferior to the 1-year freedom from MACCE in the Control arm:
 
 - $H_0: MACCE_{CONTROL} - MACCE_{PERCEVAL} \geq 0.05$ - $H_1: MACCE_{CONTROL} - MACCE_{PERCEVAL} < 0.05$ 
where $MACCE_j$ is the one-year event-free rate for arm j.
 
The primary analysis will use the Bayesian posterior probability that the difference (CONTROL – PERCEVAL valve) in 1 year MACCE event-free rates is lower than 0.05:
 $Pr(MACCE_{CONTROL} - MACCE_{PERCEVAL} < 0.05 Data)$ 
The null hypothesis will be rejected, and non-inferiority concluded, if the Bayesian posterior probability exceeds 0.9775 at the final analysis. This threshold was selected to control the Type I error rate at 2.5% (one-sided).
 
Non-inferiority will be assessed in the Per Protocol population as primary analysis. Sensitivity analyses on the primary endpoints will be performed using different assumptions and populations.
 
Interim Analysis and sample size determination
 
Total sample size for this trial will be adaptively determined through interim analyses to be performed when 900 and 1050 subjects will be enrolled. Accrual may stop earlier if there is at least 99.6% and 99.3% posterior probability of non-inferiority at the first and second interim analysis, respectively. The interim analysis will be conducted by an external Independent Statistical Unit (ISU) not involved in the study

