10.1.3 INTERIM ANALYSIS IMPUTATION MODEL

At the time of each interim analysis, there will be subjects eligible for Per Protocol analysis population whose one-year outcome is unknown (e.g. ongoing subjects not having yet reached the one-year visit). For this reason at the interim analysis an imputation model will be used for their final PP status according to these rules:

- Any subjects that are missing the one-year outcome, but are known to have a MACCE event at an intermediate visit, will have their one-year outcome imputed as “not MACCE-free”.
- Any subjects that are missing the one-year outcome but have not had a MACCE event at an intermediate visit will have their one-year outcome imputed, using multiple imputation. The probability that a subject remains MACCE-free at one year, conditional on being MACCE-free as of their last known visit, follows a Beta-Binomial distribution. A non-informative Beta(1,1) priors, separately within each arm is going to be applied. Additional details are provided in the separate Appendix 8.

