10.4.4 PER-PROTOCOL (PP) POPULATION

Per-protocol (PP) population consists of subjects without major protocol deviations and attending the scheduled follow-up visits up to 1 year at minimum. The PP population will be evaluated in terms of primary and secondary objectives.

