6.5. PER-PROTOCOL POPULATION

The “Per-Protocol” population (PP) is defined as all randomized and implanted patients attending the scheduled follow-up visits up to 1 year at minimum and without the following major protocol deviations:

- Assessment/Procedure (related to primary endpoint) Incomplete/Not Done
- Serious Adverse Event Not Reported
- No adherence to randomization allocation
- No consent obtained or if consent obtained after implant.

Further major protocol deviation may be detected by the Steering Committee and appropriately reported in the eCRF. In the exceptional event that “other” reasons requiring exclusion from the PP become apparent during the final data review, these will be suitably documented at that time in the final data review report (which will be prior to database lock).

Primary efficacy analysis will be performed on this population. The PP population will be used for analyses of primary and secondary endpoints.

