15. INTERIM ANALYSIS

Two interim analyses will be performed to select the sample size. These interims will be triggered when the number of subjects enrolled will be approximately 900 and 1050 (interim analyses cut-off dates). The study will stop accrual for expected success if the posterior probability of non-inferiority in the PP population is sufficiently high. The threshold varies by interim: accrual will stop if the posterior probability exceeds

- 0.996 at N=900, or
- 0.993 at N=1050.

The analysis will be conducted by the external Independent Statistical Unit who will communicate to the Sponsor the result of the interim analysis and the consequent decision on the continuation of enrollment (i.e. “Stop enrolment for predicted success”, “Continue enrolment”).

As the interim analyses will only determine whether accrual needs to be stopped, then the interim analyses decisions have no impact on the subsequent study conduct. Therefore subject follow up will continue up to 5 years and the primary analysis will take place at the 12-month primary analysis.

At the time of each interim analysis, there will be subjects eligible for Per Protocol analysis population whose one-year outcome is unknown (e.g. ongoing subjects not having yet reached the one-year visit). For this reason at the interim analysis an imputation model will be used for their one-year outcome according to these rules:

- Any subjects that are missing the one-year outcome, but are known to have a MACCE event at an intermediate time point, will have their one-year outcome imputed as “not MACCE-free”.
- Any subjects that are missing the one-year outcome but have not had a MACCE event at an intermediate time point (3, 6, and 9 month intervals) will have their one-year outcome imputed, using multiple imputation. The probability that a subject remains MACCE-free at one year, conditional on being MACCE-free as of their last known intermediate time point (3, 6, and 9-month intervals), follows a Beta-Binomial distribution. A non-informative Beta(1,1) priors, separately within each arm is going to be applied. Additional details are provided in the CIP Appendix 8.

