18.12. DATA DERIVATIONS

Table 8 : Data derivation rules

Derived variable	Derivation algorithm
Consented subject	Yes if filled date of consent No, otherwise.
Enrolled subject	Yes if filled date of consent AND patient is not a failure to implant (termination reason= FAILURE TO MEET RANDOMIZATION CRITERIA) No, otherwise.
ITT subject	Yes if Randomization date not empty No, otherwise.
mITT subject	Yes if ITT and the valve is a study valve (as listed in CRF). In case of "other" values, they have to be checked one by one with PM. No, otherwise.
Adherence to Randomization allocation	Yes if "Was the randomized valve implanted?" at first attempt=Yes No, otherwise.
SAF subject	Yes if Randomization and Implant dates not empty No, otherwise.
PP subject	Yes if 
 - Randomization and Implant dates not empty - Adherent to randomization - no major protocol violation (as reported in CRF field). No, otherwise.

Derived variable	Derivation algorithm
Operating room suite time (min)	Implant, Surgical time: Finish time – Start time
Skin-to-skin time (min)	Implant, Surgical time: Finish time – Start time
Extracorporeal circulation time (min)	Implant, Surgical time: Finish time – Start time
Cross clamp time (min)	Implant, Surgical time: Finish time – Start time
ICU stay (minutes)	Intensive Care Unit: [Date/Time of ICU Discharge] - [Date/Time of ICU Admission] If time of ICU discharge is missing it will be set at 23:59 If time of ICU Admission is missing it will be set at 00:00
ICU stay (days)	ICU stay (minutes) / 1440
Time to SAE	Serious Adverse Event (SAE): SAE start date – Surgery date +1
Early, Late SAE	EARLY if Time to SAE ≤ 30 days LATE if Time to SAE > 30 days

Derived variable	Derivation algorithm
Early safety (at 30 days)	
Serious Adverse Event (SAE):
 
YES if at least one (Time to SAE <=30 days) per CEC:
 
 - All-cause mortality - All stroke disabling and nondisabling - Life-threatening bleeding - Acute kidney injury—Stage 2 or 3 (including renal replacement therapy) - Coronary artery obstruction requiring intervention - Major vascular complication - Valve-related dysfunction requiring repeat procedure (BAV, TAVI, or SAVR): SVD and Aortic regurgitation requiring re-intervention 
NO, otherwise

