Clinical efficacy (after 30 days)	
Serious Adverse Event (SAE):
 
YES if at least one (Time to SAE >30 days) per CEC or Echo core lab:
 
 - All-cause mortality - All stroke (disabling and nondisabling) - Requiring hospitalizations for valve-related symptoms or worsening congestive heart failure. - NYHA class III or IV (date of assessment >30 days after valve implant) - Valve-related dysfunction: 
 i. (mean aortic valve gradient ≥ 20 mm Hg, EOA ≤ 0.9–1.1 cm² and/or DVI < 0.35 m/s, AND/OR ii. moderate or severe prosthetic valve regurgitation) 
NO, otherwise

Derived variable	Derivation algorithm
Time-related valve safety	
Serious Adverse Event (SAE):
 
YES if at least one (Time to SAE >30 days) per CEC or echo core lab:
 
 - Structural valve deterioration (both points i. and ii. have to be met): 
 i. Valve-related dysfunction: 
 ▪ mean aortic valve gradient ≥ 20 mm Hg, EOA ≤ 0.9(if BSA<1.6 cm²) or 1.1(if BSA≥ 1.6 cm²) cm² and/or DVI<0.35 m/s, AND/OR ▪ moderate or severe prosthetic valve regurgitation) ii. Requiring repeat procedure (TAVI or SAVR) - Prosthetic valve endocarditis - Prosthetic valve thrombosis - Thrombo-embolic event, non-cerebral , - TIA - STROKE - VARC bleeding (BARC type 5, BARC type 3A, 3B and 3C, BARC type 2), unless clearly unrelated to valve therapy (e.g., trauma) : Device and/or procedure related 
NO, otherwise

MACCE (Yes/No)	
Serious Adverse Event (SAE), Valve re-intervention:
 
YES if at least one per CEC:
 
 - Death - Myocardial infarction - Stroke - Reintervention 
NO, otherwise

Derived variable	Derivation algorithm
MACCE @ 1 year (Yes/No)	
Serious Adverse Event (SAE), Valve re-intervention:
 
YES if at least one per CEC:
 
 - Death (Time to SAE <=365 days) - Myocardial infarction (Time to SAE <=365 days) per CEC - Stroke (Time to SAE <=365 days) per CEC - Reintervention (Time to SAE <=365 days) 
NO, otherwise

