SAE starting date (missing)	In case of missing SAE starting date, the following rule will be applied: 
 1. If missing day: 1st day of the month 2. If missing day and month: 01-JAN 3. If totally missing: Date of surgery SAE starting date cannot be before the surgery date. In that case, SAE starting date will be set as date of surgery.
Deaths	Death is when there is a SAE: 
 - With outcome='FATAL' OR - Leading to death (SAE criteria) The date of death is retrieved from the SAE form (Date of death).
Leak severity	Leak will be classified in: 
 1. none/trace: if "Is there a Paravalvular Leak?" ("Is there a Central Leak?")='No' or severity=' Trace (<1/4+)' 2. mild: if severity=' Mild (1/4+)' 3. moderate/severe: if severity=' Moderate (2/4+)' or severity=' Severe (>= 3/4+)'

Derived variable	Derivation algorithm
Proportion of patient event-free at one year	For each MACCE component: Numerator: #patients who experienced the specific MACCE component within DAY 365 Denominator: #patients who experienced the specific MACCE component within DAY 365 + # patients without the specific event at DAY 365
Proportion of patient MACCE-free at each year	Numerator: #patients who experienced MACCE within DAY 365 (730, 1095, 1460, 1825) Denominator: #patients who experienced MACCE within DAY 365 (730, 1095, 1460, 1825) + # patients without MACCE at DAY 365 (730, 1095, 1460, 1825)
MPG Gradient class	Aortic Mean Pressure Gradient (MPG) class: 
 • MPG \geq 20mmHG • MPG < 20mmHG
Hospitalization time [days]	Discharge – Hospital Admission +1
Ward time [days]	Hospitalization time – ICU time
EQ-VAS	Use as first source of values the “EQ5D02-Your Health Today” variable. If it’s missing, use the “EQ VAS Score” to replace the missing value.
Aortic Mean Pressure Gradient (MPG) with LVOT adjustment	Aortic Mean Pressure Gradient - LVOT Mean Pressure Gradient
Peak Mean Pressure Gradient (MPG) with LVOT adjustment	Aortic Peak Pressure Gradient - LVOT Peak Pressure Gradient

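### The Per-Protocol set that decides non-inferiority requires visit attendance to 1 year with no exception for death, and the SAP's own derivation table says otherwise

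*SAP*

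**What the plan says.** The primary endpoint is one-year freedom from a composite that includes all-cause death (protocol 8.5.8; SAP 10.1). Non-inferiority is concluded if the posterior probability in the PP population exceeds 0.9775 (protocol 10.1.1; SAP 10.3).

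Three places define that population, and all three require attendance:
- Protocol synopsis: "PP population defined as all subjects without major protocol deviations and attending the scheduled follow-up visits up to 1 year at minimum".
- Protocol 10.4.4: "subjects without major protocol deviations and attending the scheduled follow-up visits up to 1 year at minimum".
- SAP 6.5: "all randomized and implanted patients attending the scheduled follow-up visits up to 1 year at minimum", and without a list of major deviations.

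SAP 18.12, Table 8, builds the PP flag from three items: randomization and implant dates, adherence to allocation, and "no major protocol violation (as reported in CRF field". Attendance is not among them.

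Other text bears on patients with an early event:
- Table 8 counts as a one-year MACCE "Death (Time to SAE <=365 days", and the denominator of its yearly proportion is "patients who experienced MACCE within DAY 365 (730, 1095, 1460, 1825) + # patients without MACCE at DAY 365".
- Protocol 10.1.3 says of PP-eligible subjects at the interim that "an imputation model will be used for their final PP status according to these rules". SAP 15 specifies that those who "are known to have a MACCE event at an intermediate time point, will have their one-year outcome imputed as" not MACCE-free.
- SAP 9 counts a missed 1-year visit as planned only after more than 395 days of follow-up.
- Protocol 18.1 lists death as a way of reaching the end of the trial, apart from premature withdrawal.

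**The concern.** A patient who dies in month 2 cannot attend the 1-year visit. Under the formal wording that patient leaves both numerator and denominator, and so does not count against the arm in which the death occurred. Under Table 8 the same patient stays and is a failure, unless the missed visit is recorded as a major deviation. Two analysts working from different sections could build different deciding sets. The interim looks would count deaths while the final analysis might not.

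The trial is open-label and sponsor personnel run the primary analysis (protocol 10), so membership of the deciding set should not be left to interpretation once outcomes are known.

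A smaller defect sits beside this. The one-year MACCE rule in Table 8 assigns NO to everyone without a recorded event. An event-free patient whose follow-up stops early is therefore scored MACCE-free if not excluded.

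**Working it through.** **Inputs from the documents.** Margin 0.05 and threshold 0.9775 (protocol 10.1.1); maximum 1234 enrolled (protocol 10.2); 10% attrition to PP (protocol 10.3); 1:1 allocation (protocol 8.5.7); event-free rates 0.91 and 0.88 (protocol Table 7). PP size per arm: 1234 x 0.9 / 2 = 555. z(0.9775) = 2.005.

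**Assumed.** One-year control mortality of 2%, 3% or 4.5%; the documents give no one-year death rates by arm. For orientation, the matched comparison of mini-sternotomy sutureless with full-sternotomy stented valves in protocol 6.2 reports 30-day deaths of 1.8% against 2.3%, and two-year survival of 91% against 93%. The death ratios, Perceval to stented, are 1.8/2.3 = 0.78 and 9/7 = 1.29.

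**Formula.** P(declare non-inferiority) = Phi[(0.05 - d)/SE - 2.005], where d is control minus Perceval event-free rate and SE is the unpooled binomial standard error.

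**The plan's own figures first, deaths counted, fixed 555 per arm.**
- 0.91 v 0.86: d = 0.05, so Phi(-2.005) = 0.0225. Exact posterior calculation 0.0233; plan 0.023.
- 0.91 v 0.91: SE = sqrt(2 x 0.91 x 0.09/555) = 0.01718; Phi(2.910 - 2.005) = 0.817. Plan 0.805.
- 0.88 v 0.83 and 0.88 v 0.88: 0.0225 and 0.712. Plan 0.025 and 0.704.

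A simulation with both interim looks gave 0.811 power and mean N 1128.6 at 0.91 in both arms (plan 0.805 and 1128.7). It assumed linear accrual over 30 months and half of the events in month 1.

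**Deaths dropped.** In each arm the event-free rate becomes 1 - (MACCE - deaths)/(1 - deaths), and n becomes 555 x (1 - deaths). Perceval MACCE is control MACCE plus 5 points.

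One case in full: control MACCE 9%, control deaths 3%, a quarter of the deficit in deaths, so Perceval deaths are 3% + 1.25% = 4.25%.
- Control: 1 - 0.06/0.97 = 0.9381, n = 538.
- Perceval: 1 - 0.0975/0.9575 = 0.8982, n = 531.
- d = 0.0400 and SE = 0.0167.
- (0.05 - 0.0400)/0.0167 = 0.60; Phi(0.60 - 2.005) = 0.080.

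Probability of false non-inferiority for control deaths of 2% / 3% / 4.5%:

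| Perceval deaths | Control MACCE 9% | Control MACCE 12% |
|---|---|---|
| Same as control | 0.020 / 0.018 / 0.016 | 0.020 / 0.019 / 0.017 |
| 9/7 of control | 0.038 / 0.052 / 0.087 | 0.035 / 0.045 / 0.069 |
| A quarter of the deficit | 0.079 / 0.080 / 0.083 | 0.066 / 0.066 / 0.066 |
| Half of the deficit | 0.237 / 0.256 / 0.298 | 0.178 / 0.186 / 0.202 |

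Simulating the planned Bayesian rule (4000 trials per case, control deaths 2% and 4.5%) agrees: 0.017-0.022 with balanced deaths, 0.069-0.087 for a quarter, 0.185-0.314 for half, and 0.020-0.025 with deaths counted.

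**Truncated event-free follow-up.** With 5-10% random loss (20,000 simulated trials), type I error is 2.2-3.2% if such patients are scored MACCE-free and 1.6-2.0% if they are dropped. A true 91.0% is estimated as 91.1-91.5% and 90.3-90.8% respectively.

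**The case against.** The strongest reply is that the working text already keeps deaths. SAP 18 exists to give implementation detail, and its PP flag has no attendance test. The interim rule scores early MACCE as failures in order to predict success of the later PP analysis, which makes little sense if those failures are then removed. A patient who has died arguably has no visit still scheduled, and SAP 9 and protocol 18.1 fit that view. Protocol 10.3 does not name death among its examples of PP attrition. This stands as evidence of intent, but it does not settle the final set. SAP 9 is a compliance denominator, the interim rule starts from patients already PP-eligible, and SAP 3.1 declares no change from the protocol, so Table 8 cannot be read as a declared replacement for protocol 10.4.4.

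The second reply is that the harm needs three things at once: the literal reading, a true 5-point deficit and excess Perceval mortality. That also stands. The 30-day ratio of 0.78 would give only about 0.3-1.3%. An excess would be visible in the mITT repeat, the Kaplan-Meier analyses and the mortality tables, although none of these is a condition for the claim.

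A reader might go further and infer that event-free dropouts must be kept in PP and imputed in the deciding analysis. The documents do not support that. Protocol 10.3 and 10.8 choose to leave them out, and dropping them is already conservative (1.6-2.0%).

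**Conclusion.** The conflict is real and should be fixed before database lock. The three formal definitions, applied as written, remove deaths from a comparison whose endpoint includes death. Table 8 and the interim rule point the other way, and no supplied text says which governs the final PP set. Appendix 8 was not supplied and may address it.

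A reader might infer that deaths will be dropped, or that the trial's type I error is 18-30% or worse. Neither follows. Deaths are probably meant to be kept, in which case the error is about 2.3% as planned. On the literal reading with balanced deaths it falls to 1.6-2.0%. At the two-year death ratio in protocol 6.2 it is about 4-9%, at a quarter of the deficit 7-8%, and at half 18-30%. All of these rest on the assumed 2-4.5% control mortality and on a true deficit equal to the margin. If the whole deficit were deaths, Perceval mortality would be 2.1-3.5 times control, and nothing in the documents suggests that.

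The scoring of truncated event-free follow-up is a minor second defect.

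**What to change.** Use one PP definition in the protocol synopsis, protocol 10.4.4, SAP 6.5 and SAP Table 8. It should state that an otherwise eligible patient with a CEC-adjudicated MACCE, including death, by day 365 meets the follow-up condition and counts as a failure whatever the visit attendance.

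In Table 8, set the one-year MACCE variable to missing, not NO, for event-free patients whose follow-up ends before 1 year. They can stay outside PP, as protocol 10.3 and 10.8 imply, with imputation left to the mITT sensitivity analysis already planned in SAP 10.4.

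The cost is one sentence in four places and one derivation rule, with the related protocol amendment or SAP change note. No new data are needed. If deaths were always to be kept, the first change alters no result.

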16.1 PROTOCOL DEVIATIONS

Investigators of the trial are not allowed to deviate from the protocol requirements. In particular, it is recommended to make every effort to avoid introduction of biases caused by protocol deviations. If a deviation should occur it shall be listed and reported in the appropriate eCRF.

The Sponsor will assess the seriousness of the deviation classifying these as major or minor; and will present the list of the deviations to the Steering Committee (SC). The final decision about the seriousness will be taken by the SC.

Major deviations are defined as changes in the conduct of the trial different from what is specified in the protocol that may potentially compromise the subject's rights, safety, and well-being, or the completeness, accuracy, reliability, or scientific integrity of the trial data. Accrual of major deviations by a site may lead to no further participation within the study as reported in section 18.3.

Major and minor deviations will be validated before data lock and prior to the statistical analysis being performed.

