17.2 INVESTIGATOR’S RESPONSIBILITIES IN AE REPORTING

- a) The Principal investigator is required to report the following serious adverse events to the Sponsor:
- All MACCE (deaths, MI, Stroke and valve re-intervention) and USADEs throughout the trial duration up to 5 years.
 - All other serious adverse events up to 5 years including: structural valve deterioration, non-structural valve dysfunctions, endocarditis, thromboembolic events, and valve thrombosis.

Table 10 Adverse Events Reporting to the Sponsor

	Subject Visit					
	Point of enrollment	Implant	Discharge	Late Post-op (1-3 Mo.)	1 Year (11-13 Mo.)	Annual Follow-up
All Deaths, USADE, SAE	x	X	X	X	X	X

The following timelines for reporting should be followed (**Table 11**):

- Unanticipated Serious Adverse Device Effects (USADE) should be reported to the Sponsor immediately within 24 hours by notifying the Sponsor Clinical Project Manager and by entering the information in the EDC. These events require urgent investigation by the Sponsor and reporting to regulatory authorities, as applicable.
- Serious adverse events should be reported as soon as possible but no later than 3 calendar days upon awareness. The investigator should enter all available information in the SAE section of the EDC system.
- Device deficiencies should be reported within 3 calendar days of awareness. Deficiencies of the Sorin study device should be reported in the EDC. The investigator must return the device, if possible, to the Sponsor. Deficiencies of the non-Sorin study device should be reported following the commercial reporting procedure for that device.

Table 11 Timelines and Communication Methods for Reporting Serious Adverse Events

Event Classification	Communication Method	Communication Timeline
USADE	Contact Clinical Project Manager Complete AE eCRF page with all available information.	Within 24 hours of awareness
Serious Adverse Event including deaths and SADE Device Deficiencies (including but not limited to failures, malfunctions, and product nonconformities including labeling and packaging issues)	Complete AE eCRF page with all available information.	Within 3 calendar days of first becoming aware of the event or as per local/regional regulations. Reporting of any updated information required through the end of the trial
	Provide all relevant source documentation (unidentified) for reported event	When documentation is available

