7.3. PROTOCOL DEVIATIONS

All protocol deviations (PDs) will be summarized overall (ENR) and by arm (ITT) by severity (minor and major) and grouped into different categories:

- Inclusion/Exclusion
- Informed Consent
- Procedure Performed by Unauthorized Physician
- Visit/Follow-up Not Done

- Visit/Follow-up Out of Window
- Assessment/Procedure Incomplete/Not Done
- Assessment/Procedure Out of Window
- Planned Surgical Approach Changed
- Randomization
- Study Device Not Used per IFU or per Protocol
- Serious Adverse Event Not Reported per Protocol
- Other

PDs will be reported as:

- total PDs on the total number of patients
- number of subjects with at least one PD on the total number of patients

Protocol deviations will be presented in a subject data listing.

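### The Per-Protocol exclusion for an unreported serious adverse event lets known MACCE patients drop out of the deciding analysis; the direction and size of the resulting bias are not fixed by the documents

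*SAP*

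**What the plan says.** SAP 6.5 defines PP as randomized and implanted patients who attend visits to at least one year and have none of four listed major deviations. One of the four is "Serious Adverse Event Not Reported". The same section states: "Primary efficacy analysis will be performed on this population". SAP 10.2 and 10.3 confirm that the non-inferiority test is run on PP, and SAP 15 uses the PP posterior probability for the accrual-stopping decision.

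Protocol 17.2 puts the primary endpoint events among the serious adverse events to be reported: "All MACCE (deaths, MI, Stroke and valve re-intervention) and USADEs throughout the trial duration up to 5 years". It also sets a time limit: "Serious adverse events should be reported as soon as possible but no later than 3 calendar days upon awareness".

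The deviation table in SAP 7.3 words the category differently, as "Serious Adverse Event Not Reported per Protocol". In SAP 18.12, Table 8, the PP flag requires "no major protocol violation (as reported in CRF field", with no exception for a patient whose MACCE is known. On who decides, Protocol 16.1 says "The Sponsor will assess the seriousness of the deviation classifying these as major or minor", and then "The final decision about the seriousness will be taken by the SC".

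SAP 10.4 repeats the primary analysis on the mITT population, and runs the Kaplan-Meier analysis on PP and mITT, as sensitivity analyses.

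**The concern.** Membership of the deciding analysis set should not depend on whether the patient had the outcome. This exclusion does depend on it: a patient without any SAE cannot incur the deviation, while a patient with a death, stroke, infarction or re-intervention can. The deviation can be logged only after someone learns of the event, and by then the event can in principle be entered and sent to the Clinical Events Committee (CEC). The plan does not say that this restores the patient to PP.

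At stake is the 2.5% one-sided error rate. With about 50 control and 78 Perceval MACCE patients expected at the margin, losing a handful can move the result. If similar shares are lost in both arms and MACCE patients are hit more often than MACCE-free patients, the arm with more events loses more of them, and the observed difference shrinks toward non-inferiority.

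**Working it through.** **Inputs from the documents.** Margin 0.05 and success threshold 0.9775 (SAP 10.3); maximum 1234 patients, 1:1 (Protocol 8.1, SAP 2.4); 10% attrition to PP (Protocol 10.3), so 1234 × 0.9 / 2 ≈ 555 per arm; event-free rates 0.91 vs 0.86 at the margin (SAP 2.3, Table 1).

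**Assumptions, not in the documents.** f is the share of MACCE patients removed. s is the share of MACCE-free patients who have an SAE; they are removed at the same rate f, so a share g = s × f of MACCE-free patients is lost.

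**Reproducing the plan's figures.** Normal approximation, fixed N, no interim looks, z(0.9775) = 2.0047. With 0.91 in both arms, SE = √(2 × 0.91 × 0.09 / 555) = 0.01718, and power = Φ(0.05/0.01718 − 2.0047) = 0.817, against the stated 0.805. With 0.88 in both arms the result is 0.712, against 0.704. At 0.91 vs 0.86 the error is 1 − 0.9775 = 2.25%, against the stated 0.023. A fixed-N simulation with the SAP's prior gives power 0.816 and error 0.024. The approximation is close enough for this purpose.

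**Effect of the exclusion.** For an arm with event rate q (0.09 control, 0.14 Perceval):

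- remaining n′ = 555 × [(1−q)(1−g) + q(1−f)]
- event-free rate p′ = 555 × (1−q)(1−g) / n′
- d = p′(control) − p′(Perceval), with SE from the two binomial variances
- false-claim rate = Φ((0.05 − d)/SE − 2.0047)

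Example, f = 10%, s = 0: control events 49.95 → 44.955, p′ = 505.05/550.005 = 0.91826. Perceval events 77.7 → 69.93, p′ = 477.3/547.23 = 0.87221. So d = 0.04605, SE = 0.01844, and Φ(0.214 − 2.0047) = 3.7%.

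Same f in both arms:

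| f | d (s = 0) | false-claim rate (s = 0) | d (s = 30%) | false-claim rate (s = 30%) |
|---|---|---|---|---|
| 0 | 0.0500 | 2.25% | 0.0500 | 2.25% |
| 2% | 0.0492 | 2.5% | 0.0495 | 2.4% |
| 5% | 0.0481 | 2.9% | 0.0486 | 2.7% |
| 10% | 0.0461 | 3.7% | 0.0472 | 3.2% |
| 20% | 0.0419 | 6.1% | 0.0440 | 4.6% |

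If every patient had an SAE (s = 1), equal f would leave the rates unchanged.

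Other patterns:

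| Removal | d | false-claim rate |
|---|---|---|
| 10% of MACCE patients, Perceval only | 0.0378 | 8.8% |
| 10% of MACCE patients, control only | 0.0583 | 0.7% |
| 5 MACCE patients from each arm | 0.0505 | 2.1% |
| 2% of MACCE and 5% of MACCE-free, both arms | 0.0512 | 1.9% |

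**The case against.** Much can be said for the plan.

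- **The rule is not aimed at MACCE.** It covers all SAEs, so some event-free patients go too. Major events may also be missed less often than other SAEs: SAP 4.5 provides listings of cardiac markers, ECG, mRS and NIHSS results to screen for adjudicable events. If MACCE-free patients were removed more often than MACCE patients, the bias would reverse (last row above). This stands, and it is why no fixed direction can be claimed. A reader might infer that the rule necessarily shrinks the arm difference; the documents do not support that.
- **Late reports.** A reader might infer that a stroke entered on day 4 leaves PP. SAP 6.5 speaks only of events not reported. The wider wording is in SAP 7.3, which tabulates minor as well as major deviations. Removal needs a major classification under Protocol 16.1, and Protocol Table 11 also allows local or regional timelines. Whether lateness counts is unclear, not settled.
- **Knowledge of treatment arm.** The trial is non-blinded, so a reader might infer that deviations are classified with the arm in view. The available text does not say what the Steering Committee sees, and Protocol 16.1 requires validation before lock.
- **Data quality.** Table 8 codes MACCE as no unless an adjudicated event is present. Retaining a patient whose event was never adjudicated could count a true event as event-free. This is a fair rationale for caution, and the fix has to deal with it.
- **Visibility.** The mITT repeat, the deviation tables by arm and the MACCE listing would show a material loss. They would reveal a discrepancy but would not decide the claim.
- **Attrition.** The calculation removes patients on top of the 10% allowance, which may already include some of them. This affects size only slightly.

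None of this supplies a rule that keeps a known, adjudicated MACCE patient in PP.

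**Conclusion.** The defect holds as a matter of definition: the primary set contains an exclusion that only patients with an SAE can meet, and it can remove known primary events. Its effect is conditional. With equal proportional removal of 5% to 20% of SAE patients in both arms, the false-claim rate is 2.9% to 6.1% if no MACCE-free patient is affected, and 2.7% to 4.6% if 30% of them also have an SAE. Removal confined to one arm can take it well above or well below the nominal 2.5%, and 2% or less in both arms leaves it within that limit. These figures rest on the normal approximation, a true difference exactly at the margin, no interim looks, and assumed values of f and s that the documents do not give. The point should be fixed before lock; the documents do not show that the primary conclusion is in fact biased.

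**What to change.** Delete "Serious Adverse Event Not Reported" from the exclusion list in SAP 6.5. Add to the PP flag in SAP 18.12, Table 8, that SAE-reporting deviations, whether late or missed, do not remove a patient from PP. Before lock, enter every SAE found in this way, send it to the CEC and count the patient by the adjudicated result, so that an unadjudicated event does not fall through to the MACCE-no default. Apply the same definition at the interim analyses. Keep the deviation in the SAP 7.3 tables, where it serves to monitor site quality.

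The cost is one deleted line, one added clause and the adjudication of the events concerned. The PP set becomes slightly larger and the event-free rates slightly lower. No new sample size is needed.
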